### 9.3.4. Potential Drug-Induced Liver Injury Events

According to FDA's guidance on drug-induced liver injury (2009), the criteria for potential DILI events include the following:

- ALT ≥ 3 × ULN
- ALT ≥ 5 × ULN
- ALT ≥ 10 × ULN
- ALT ≥ 20 × ULN
- AST ≥ 3 × ULN
- AST ≥ 5 × ULN
- AST ≥ 10 × ULN
- AST ≥ 20 × ULN

- ALT or AST  $\geq 3 \times$  ULN
- ALT or AST  $\geq 5 \times$  ULN
- ALT or AST  $\geq 10 \times$  ULN
- ALT or AST  $\geq 20 \times$  ULN
- ALP  $\geq 1.5 \times$  ULN
- Total bilirubin  $\geq 2 \times$  ULN
- ALT and/or AST  $\geq 3 \times$  ULN and total bilirubin  $\geq 2 \times$  ULN

Note that the combination of values needs to be measured on the same day.

The number and percentage of participants with postbaseline liver-specific function test values that meet these criteria will be presented at each scheduled visit by treatment group. Participants with potential DILI events will also be listed.

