6.6.1. Criteria and Procedures for Dose Interruptions and Adjustments of Study Drug

Safety concerns should be discussed with the sponsor immediately upon occurrence or awareness to determine if the participant should continue or discontinue study drug.

Treatment with study drug may be interrupted for up to 28 days, unless otherwise specified in the Protocol or a longer period is approved by the sponsor (or designee), to allow for resolution of toxicity. The principal investigator (or designee) should contact the sponsor to discuss the case of any participant whose treatment has been interrupted for more than 21 days (but less than 28 days) before restarting treatment. Participants may resume treatment if no medical condition or other circumstance exists that, in the opinion of the investigator, would make the participant unsuitable for further participation in the study.

Guidelines for interruption, restarting, and discontinuation of study drug are outlined in [Table 8](#) as well as in [Appendix E](#) (for COVID-19) and Section 6.6.1.6 (for emergency and elective surgeries).

Table 8: Guidelines for Interruption, Restarting, and Discontinuation of Study Drug

Laboratory Value	Action Taken
Chemistry	
ALT and/or AST is $> 3.0 \times < 20$ ULN	
Step 1: Interrupt study drug.
 
Step 2: Confirm whether potential Hy's law criteria have been met (see Appendix D), following applicable procedures. If potential Hy's law criteria are not met, proceed to Step 3.
 
Step 3: Repeat ALT/AST assessments weekly for up to 3 weeks or until ALT and/or AST results are $< 3.0 \times$ ULN and then restart study drug at the same dose.
 
If ALT and/or AST result(s) do not decrease to $< 3.0 \times$ ULN after 3 weeks of drug interruption, study drug will be permanently discontinued, and the participant will follow EOT visit procedures; a post-treatment follow-up visit (EOS) is also recommended.
 
If the dose has been interrupted/restarted in 2 other instances due to ALT and/or AST results, and ALT and/or AST results are $> 3.0 \times$ ULN for a third time, study drug will be permanently discontinued, and the participant will follow EOT visit procedures; a post-treatment follow-up visit (EOS) is also recommended.
 
In parallel to the participant starting the post-treatment follow-up period, the investigator, in collaboration with the medical monitor, will determine further steps.

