8.6. Unscheduled Visits

Unscheduled visits may occur as clinically indicated. Any assessments performed at those visits should be recorded in the eCRF and noted as an unscheduled visit.

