8.7. End of Treatment and Early Termination

The EOT1 (PC period) coincides with the Week 12 visit, and the EOT2 (EXT period) coincides with the Week 36 visit. A participant who completes the Week 12/EOT1 visit will have completed the PC period and may continue into the EXT period. A participant who completes the Week 36/EOT2 visit will have completed the EXT period.

If a decision is made that the participant will permanently discontinue study drug prior to the Week 36/EOT2 visit, then the ET visit should be conducted and will be determined as ET1 (if during the PC period) or ET2 (if during the EXT period). If the ET visit coincides with a regular study visit, then the ET evaluations will supersede those of that scheduled visit, and the data should be entered in the ET visit in the eCRF. If this decision does not coincide with a regular visit, reasonable efforts should be made to have the participant return to the site to complete the ET procedures. The participant should be encouraged to return for the follow-up visit.

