### 9.3.3. Potentially Clinically Important Laboratory Values

Criteria for potentially clinically important laboratory values are listed in [Table 8](#). The number and percentage of participants with postbaseline laboratory values that meet each criterion will be summarized at each scheduled visit by treatment group. Participants with potentially clinically important laboratory values will also be listed.

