3.3.2.3.1	Shift Summary of Lipid Panel Laboratory Values - to the Worst Abnormal Value	Safety	X
3.3.3.1.x	Shift Summary of Hematology Laboratory Values in CTCAE Grade - to the Worst Grade Abnormal Value	Safety/EXT-Evaluable	X
3.3.3.2.x	Shift Summary of Chemistry Laboratory Values in CTCAE Grade - to the Worst Grade Abnormal Value	Safety/EXT-Evaluable	X
3.3.3.3.1	Shift Summary of Lipid Panel Laboratory Values in CTCAE Grade - to the Worst Grade Abnormal Value	Safety	X

Table No.	Title	Population	Standard
3.3.4.x	Summary of Potentially Clinically Important Laboratory Values by Visit	Safety/EXT-Evaluable	X
3.3.5.x	Summary of Potential Drug-Induced Liver Injury Events by Visit	Safety/EXT-Evaluable,	
3.4.1.x	Summary of Systolic Blood Pressure During the PC Period	Safety/EXT-Evaluable	X
3.4.2.x	Summary of Diastolic Blood Pressure During the PC Period	Safety/EXT-Evaluable	X
3.4.3.x	Summary of Pulse During the PC Period	Safety/EXT-Evaluable	X
3.4.4.x	Summary of Respiratory Rate During the PC Period	Safety/EXT-Evaluable	X
3.4.5.x	Summary of Body Temperature During the PC Period	Safety/EXT-Evaluable	X
3.5.1.1.x	Summary of PR Interval (ms) From 12-Lead ECG by Visit During the PC Period	Safety/EXT-Evaluable	X
3.5.1.2.x	Summary of QRS Interval (ms) From 12-Lead ECG by Visit During the PC Period	Safety/EXT-Evaluable	X
3.5.1.3.x	Summary of QT Interval (ms) From 12-Lead ECG by Visit During the PC Period	Safety/EXT-Evaluable	X
3.5.1.4.x	Summary of QTcF Interval (ms) From 12-Lead ECG by Visit During the PC Period	Safety/EXT-Evaluable	X
3.5.1.5.x	Summary of Heart Rate (bpm) From 12-Lead ECG by Visit During the PC Period	Safety/EXT-Evaluable	X
3.5.1.6.x	Summary of Clinically Significant ECG Abnormality by Visit During the PC Period	Safety/EXT-Evaluable	X

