### Listings

Listing No.	Title
2.1.1	Participant Enrollment and Disposition Status
2.1.2	Participant Inclusion and Exclusion Criteria Violations
2.2	Protocol Deviations
2.3	Analysis Populations
2.4.1	Demographic and Baseline Characteristics
2.4.2	Disease History
2.4.3	Prior Therapy for Chronic Spontaneous Urticaria
2.4.4	Medical History
2.4.5	Prior and Concomitant Medications
2.5.1	Study Drug Exposure and Compliance
2.7.1	Adverse Events
2.7.2	Serious Adverse Events
2.7.3	Grade 3 and Higher Adverse Events
2.7.4	Fatal Adverse Events
2.7.5	Treatment-Related Adverse Events
2.7.6	Adverse Events Leading to Dose Interruption
2.7.7	Adverse Events Leading to Discontinuation of Study Drug
2.7.8	Adverse Events of Special Interest
2.7.9	Events of Clinical Interest
2.8.1.1	Clinical Laboratory Values - Hematology
2.8.1.2	Clinical Laboratory Values - Chemistry
2.8.1.3	Clinical Laboratory Values - Lipid Panel
2.8.2.1	Abnormal Clinical Laboratory Values - Hematology

Listing No.	Title
2.8.2.2	Abnormal Clinical Laboratory Values - Chemistry
2.8.2.3	Abnormal Clinical Laboratory Values - Lipid Panel
2.8.3	Potentially Clinically Important Laboratory Values During the PC Period
2.8.4	Potential Drug-Induced Liver Injury Events During the PC Period
2.9.1	Vital Signs
2.9.2	Abnormal Vital Sign Values
2.9.3	Alert Vital Sign Values
2.10.1	12-Lead ECG Values
2.10.2	Abnormal 12-Lead ECG Values
2.10.3	Alert 12-Lead ECG Values

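### SAP 9.3.4 counts potential liver-injury criteria only at scheduled visits, so a participant who first meets a higher tier or the combined criterion at a weekly repeat test is missing from that row, and no any-time count is stated

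*SAP*

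**What the plan says.** SAP 9.3.4 lists liver criteria at 3, 5, 10 and 20 × ULN for ALT, for AST and for either one. It adds ALP, total bilirubin, and a combined criterion: ALT and/or AST at least 3 × ULN with total bilirubin at least 2 × ULN on the same day. The counts "will be presented at each scheduled visit by treatment group". The planned output is Table 3.3.5.x, "Summary of Potential Drug-Induced Liver Injury Events by Visit". SAP 9.3.3 treats its own list the same way: results "will be summarized at each scheduled visit by treatment group", in Table 3.3.4.x, "Summary of Potentially Clinically Important Laboratory Values by Visit". Neither section mentions a count over all postbaseline values.

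The protocol's schedule of activities has chemistry and hematology at every visit, 4 weeks apart during treatment with a window of ±3 days. After a raised ALT/AST result, protocol Table 8 (Section 6.6.1) says: "Repeat ALT/AST assessments weekly for up to 3 weeks", or until recovery. For unscheduled visits, protocol 8.6 says: "Any assessments performed at those visits should be recorded in the eCRF and noted as an unscheduled visit". If early termination coincides with a regular visit, "then the ET evaluations will supersede those of that scheduled visit, and the data should be entered in the ET visit in the eCRF" (protocol 8.7).

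**The concern.** The repeat tests happen because a value was abnormal, so the results most likely to hold the peak are the ones a scheduled-visit table does not use. The first raised value usually comes from a scheduled visit, so the 3 × ULN rows should be largely complete. The rows at risk are the higher tiers and the combined ALT/AST-plus-bilirubin criterion.

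There is a second problem, which exists even without unscheduled tests. A participant above a threshold at two visits is counted in two rows, so by-visit counts do not give the number who ever met the criterion. A dose-ranging safety comparison between arms needs that number, and the protocol's benefit/risk section already treats the JAK inhibitor class as needing close safety monitoring.

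**Working it through.** The plan states no figure on this point, so there is none to reproduce. The check is timing arithmetic followed by a comparison of outputs.

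**1. Do the repeats fall between scheduled visits?** Inputs: 28 days between treatment visits and a ±3-day window (schedule of activities); weekly repeats for up to 3 weeks (protocol Table 8).

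- Gap between two scheduled visits = 28 ± (3 + 3) = 22 to 34 days.
- Repeats counted from the scheduled sample fall on days 7, 14 and 21. All three come before day 22, so 3 of 3 precede the next visit even at the shortest gap.
- If the repeats start a week late, they fall on days 14, 21 and 28. Two of the three still precede the shortest gap.

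**2. Can the SAP bring them in?** SAP 4.1 has no window rule that assigns an unscheduled result to a scheduled visit. If one were applied, the rule in SAP 9.3.2 for several values at one visit takes the central laboratory value, then the smallest sequence number. It does not take the worst value.

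**3. Illustration (invented values).** Week 4: ALT 4 × ULN, bilirubin normal. Repeat on day 7: ALT 12 × ULN, bilirubin 2.5 × ULN. Week 8: both below every threshold. AST and ALP stay normal.

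- Criteria ever met: ALT at 3, 5 and 10 × ULN (3 rows), ALT or AST at 3, 5 and 10 × ULN (3), bilirubin (1), combined (1) = 8.
- Criteria shown by visit: ALT at 3 × ULN and ALT or AST at 3 × ULN, both at Week 4 = 2.
- Missing from the table: 8 − 2 = 6, including the combined criterion.

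**4. Additivity.** One participant at or above 3 × ULN at Weeks 4 and 8 contributes 1 + 1 = 2 to the by-visit rows but 1 to the number ever affected.

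**5. What the other outputs supply.**

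| Output | Covers | Does not supply |
|---|---|---|
| Clinical-interest laboratory outliers (SAP 9.2.4) | ALT/AST above 5 × ULN, with no scheduled-visit limit | The 10 × ULN tier or bilirubin; may be a listing only |
| Worst-grade shifts (SAP 9.3.2) | Worst postbaseline grade for each analyte | A same-day combination, or an either-ALT-or-AST count |
| Adverse event tables | Participants whose drug was interrupted or stopped, by preferred term | Threshold counts |
| Hy's law output (SAP 9.3.5, Figure 4.5.3) | The combination at the same visit, scheduled or not | A stated count; cases with ALP above 2 × ULN |
| Chemistry and abnormal-chemistry listings (2.8.1.2, 2.8.2.2) | Individual values | Any count |

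The SAP does not say whether the CTCAE bands used in the shift tables break at 10 × ULN. SAP Table 8 ends Grade 3 for ALT and AST at 10 × ULN. If the shifts used those bands, the worst grade would approximate the tier for each analyte separately, but still not for ALT or AST together.

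**6. Size per participant missed.** With 34 per arm, 1/34 = 2.9 percentage points and 2/34 = 5.9. In the extension, placebo participants are split 1:1:1, so about 34/3 ≈ 11 enter each switch group, and 1/11 ≈ 9 percentage points.

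**The case against.** The best defence is that the report as a whole covers most of this. A reader might infer that peak values disappear, or that the report understates a liver signal. The documents do not support that. SAP 9.2.4 asks for all participants with outlier ALT, AST, creatinine or CPK values. The shift tables go to the worst postbaseline grade. Protocol 9.1 makes a laboratory abnormality an adverse event when it requires a change in study drug, and protocol Table 8 interrupts drug for the ALT/AST elevations that trigger the repeats. Those participants should therefore appear in Tables 3.2.15.x or 3.2.16.x. This part of the defence stands, and it limits the point to stated counts in one table.

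Three further inferences go too far.

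- *Early-termination results are excluded.* The schedule of activities places ET1 and ET2 in the Week 12 and Week 36 columns, so they may be tabulated there. The SAP has no rule either way.
- *Extension cases go unlisted.* Listing 2.8.4 is titled "Potential Drug-Induced Liver Injury Events During the PC Period", and Listing 2.8.3 has the same period in its title. But SAP 9.1 applies the safety analyses to the extension and overall periods, SAP 9.3.3 and 9.3.4 promise listings with no period limit, and Appendix A describes itself as guidelines. The titles need aligning; they do not prove an omission.
- *SAP 9.3.3 has an equal gap.* Its criteria each concern one analyte, so the worst-grade shifts largely cover them.

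Finally, the table shells are in a separate document and may already contain an overall row. That is possible, but the SAP text should state it.

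**Conclusion.** The point holds for the counts in SAP 9.3.4. As written, Table 3.3.5.x misses a participant who first meets a higher tier or the combined criterion at a weekly repeat test, and its rows cannot be summed to an incidence. What remains after allowing for the other outputs is narrow: no count by arm is stated for the same-day ALT/AST-plus-bilirubin criterion irrespective of ALP, or for the 10 × ULN tier. The ALP restriction matters because protocol Appendix D identifies potential Hy's law cases regardless of ALP.

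Each participant missed is worth about 2.9 percentage points in a randomized arm and about 9 in a placebo-switch group. How many would be missed cannot be estimated, because the documents give no event rate; it could be none. The conclusion assumes that Table 8 repeats are recorded as unscheduled visits, as protocol 8.6 implies, and that the shells add no overall row. This is a low-cost improvement and does not threaten the trial's conclusions.

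**What to change.** - In SAP 9.3.4, add for each period an any-time-postbaseline row that counts each participant once per criterion over all scheduled, unscheduled, early-termination and follow-up values. Keep the same-day rule for the combined criterion, and keep the by-visit rows.
- Add the same row in SAP 9.3.3 for consistency. This has lower priority.
- Retitle Listings 2.8.3 and 2.8.4 so that they match the SAP text and cover all periods.

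The cost is a few lines of SAP text and minor programming on data already collected, with no burden on sites or participants. The counts may come out slightly less favourable than the by-visit rows.

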### 9.3.5. Potential Hy's Law Events

Participants with elevated ALT or AST  $\geq 3 \times$  ULN and ALP  $\leq 2 \times$  ULN accompanied by total bilirubin  $> 2 \times$  ULN at the same visit will be listed and plotted by treatment group.

## 9.4. Vital Signs

At each scheduled visit, change, and percentage change from baseline for vital signs, including systolic blood pressure, diastolic blood pressure, pulse, temperature, respiratory rate, and weight, will be summarized descriptively. Baseline will be determined according to Section 4.1.3.

Normal ranges for vital sign values are defined in Table 9. For participants exhibiting vital sign abnormalities, the abnormal values will be listed along with their assigned treatment group. Alert vital signs are defined as an absolute value outside the defined normal range and percentage change  $> 25\%$ . Note that the definition of alert vital signs does not apply for body temperature and weight. The abnormal values for participants exhibiting alert vital sign abnormalities will be listed.

**Table 9: Normal Ranges for Vital Sign Values**

Parameter	High Threshold	Low Threshold
Systolic blood pressure	$\leq 155$ mm Hg	$\geq 85$ mm Hg
Diastolic blood pressure	$\leq 100$ mm Hg	$\geq 40$ mm Hg
Pulse	$\leq 100$ bpm	$\geq 45$ bpm
Temperature	$\leq 38^\circ\text{C}$	$\geq 35.5^\circ\text{C}$
Respiratory rate	$\leq 24$ breaths/min	$\geq 8$ breaths/min

## 9.5. Electrocardiograms

Twelve-lead ECGs, including PR, QT, QRS, and QTcF intervals, will be obtained for each participant during the study. Values at each scheduled visit, change, and percentage change from baseline will be summarized for each ECG parameter. Baseline will be determined as the average of all nonmissing values before the first administration of povorcitinib or placebo.

Normal ranges for ECG values are defined in Table 10. The ECG values will also be considered abnormal if the absolute percentage change from baseline is > 25% (30% for QRS interval). Participants exhibiting ECG abnormalities will be listed with study visit and assigned treatment group. Abnormal values for participants with alert ECG values, defined as both the absolute value and the percentage change from baseline being outside normal ranges, will be identified and listed. Outliers of QT and QTcF values, defined as absolute values > 450 milliseconds, > 500 milliseconds, or change from baseline > 30 milliseconds, will be summarized.

**Table 10: Normal Ranges for Electrocardiogram Intervals**

Parameter	High Threshold	Low Threshold
PR	$\leq 220$ ms	$\geq 75$ ms
QT	$\leq 500$ ms	$\geq 300$ ms
QRS	$\leq 120$ ms	$\geq 50$ ms
QTcF	$\leq 450$ ms	$\geq 295$ ms

## 10. INTERIM ANALYSES

No formal interim analysis is planned in this study. However, preplanned analyses of safety will be provided to an internal DMC as specified in the DMC charter. The process by which the DMC will review data and make recommendations and decisions will be documented in the DMC charter.

### 10.1. Overview of Interim Analyses

No formal interim analysis is planned in this study.

## 11. CHANGES AND MODIFICATIONS TO THE ANALYSIS PLAN

All versions of the SAP are listed in [Table 11](#).

**Table 11: Statistical Analysis Plan Versions**

SAP Version	Date
Version 1	20 MAR 2025

### 11.1. Changes to Protocol-Defined Analyses

The endpoint language in the Protocol referring to the following endpoints is not correctly worded for an endpoint.

[figure not shown]
- AEs, assessed by changes in vital signs and ECGs and through clinical laboratory sample evaluations and the results of physical examinations
- Proportion of participants who achieve  $UAS7 \leq 6$  (controlled disease) at Week 12
- Proportion of participants with  $ISS7/HSS7/UAS7 = 0$  at Week 12
- Proportion of participants who achieve  $UAS7 \leq 6$  at Week 12 and maintain or improve their response at every visit through to Week 36 or EOT2
- Proportion of participants who achieve  $UAS7 = 0$  at Week 12 and maintain their response at every visit through to Week 36 or EOT2
- [REDACTED]
- Proportion of participants requiring treatment of CSU with corticosteroids from baseline up to Week 36
- Proportion of participants requiring rescue treatment of CSU with additional second-generation H1 antihistamine from baseline up to Week 36
- Proportion of participants using rescue medication during the post-treatment follow-up period (EOT2 to EOS)
- [REDACTED]
- [REDACTED]

The endpoint should specify participant-level data to be analyzed, such as

- TEAEs and changes in clinical laboratory evaluations, vital signs, ECGs, and physical examination findings
- $UAS7 \leq 6$  (controlled disease) at Week 12
- $ISS7/HSS7/UAS7 = 0$  at Week 12
- $UAS7 \leq 6$  at Week 12 and maintenance or improvement of response at every visit through to Week 36 or EOT2.
- $UAS7 = 0$  at Week 12 and maintenance of response at every visit through to Week 36 or EOT2

- [REDACTED]
- Participants requiring treatment of CSU with corticosteroids from baseline up to Week 36
- Participants requiring rescue treatment of CSU with additional second-generation H1 antihistamine from baseline up to Week 36
- Participants requiring rescue medication usage during the post-treatment follow-up period (EOT2 to EOS)
- [REDACTED]
- [REDACTED]

In future protocols, this language will be updated to better reflect the participant-level data for the analyses.

## **11.2. Changes to the Statistical Analysis Plan**

Not applicable.

## APPENDIX A. PLANNED TABLES, FIGURES, AND LISTINGS

This appendix provides a list of the planned tables, figures, and listings for the CSR. Shells are provided in a separate document for tables that are not in the most current Standard Safety Tables. In-text tables are identical in structure and content as appendix tables but follow a Rich Text Format.

The list of tables, figures, and listings are to be used as guidelines. Modifications of the lists that do not otherwise affect the nature of the analysis will not warrant an amendment to the SAP.

### Tables

Table No.	Title	Population	Standard
1.1.1	Analysis Populations	All Screened	X
1.1.1.1	Screening Disposition	All Screened	X
1.1.2.x	Summary of Participant Disposition During the PC Period	FAS/EXT-Evaluable	X
1.1.3	Summary of Number of Participants Enrolled by Country and Site	FAS	X
1.1.4.x	Summary of Protocol Deviations During the PC Period	FAS/EXT-Evaluable	X
1.2.x	Summary of Demographics and Baseline Characteristics During the PC Period	FAS/EXT-Evaluable	X
1.3.1	Summary of Baseline Disease Characteristics	FAS	X
1.4.1	Summary of Prior Medications	FAS	X
1.4.2	Summary of Concomitant Medications During the PC Period	FAS/EXT-Evaluable	X
1.5.1	Summary of General Medical History	FAS	X
1.5.2	Summary of Chronic Spontaneous Urticaria Disease History	FAS	X
Efficacy			
2.1.1.x	Summary and Analysis of UAS7 by Visit	FAS/EXT-Evaluable	
2.1.2	Summary of UAS7 by Visit and Sex	FAS	
2.1.3	Summary of UAS7 by Visit and Geographic Region	FAS	
2.1.4	Summary of UAS7 by Visit and Baseline Anti-IgE Biologic Use	FAS	
2.2.1.1.x	Summary and Analysis of Proportion of Participants Who Achieved UAS7 $\leq$ 6 (Controlled Disease) by Visit	FAS/EXT-Evaluable	
2.2.1.2	Summary of Time to First Achievement of UAS7 $\leq$ 6 (Controlled Disease) During the PC Period	FAS	
2.2.1.3.x	Summary and Analysis of Proportion of Participants With UAS7 = 0 by Visit	FAS/EXT-Evaluable	
2.3.1.1.x	Summary of Change From Baseline in HSS7 by Visit	FAS/EXT-Evaluable	
2.3.1.2.x	Summary of Proportion of Participants With HSS7 = 0 by Visit	FAS/EXT-Evaluable	
2.3.1.3	Summary of Time to First Achievement of HSS7 MID ( $\geq$ 5-Point) Improvement From Baseline Up to Week 36	FAS	

Table No.	Title	Population	Standard
2.3.1.4	Summary of Change From Baseline in Weekly HSS7 During the Post-Treatment Follow-Up Period (EOT2 to EOS)	Post-Treatment-Evaluable	
2.3.2.1.x	Summary of Change from Baseline in ISS7 by Visit	FAS/EXT-Evaluable	
2.3.2.2.x	Summary of Proportion of Participants with ISS7 = 0 by Visit	FAS/EXT-Evaluable	
2.3.2.3	Summary of Time to First Achievement of ISS7 MID ( $\geq$ 5-Point) Improvement From Baseline Up to Week 36	FAS	
2.3.2.4	Summary of Change From Baseline in Weekly ISS7 During the Post-Treatment Follow-Up Period (EOT2 to EOS)	Post-Treatment-Evaluable	
2.3.4.1	Summary of Time to First Achievement of UAS7 $\geq$ 9.5-Point Improvement From Baseline Up to Week 36	FAS	
2.3.4.2	Summary of Proportion of Participants Who Achieved UAS7 $\leq$ 6 at Week 12 and Maintained or Improved Their Response at Every Visit Through to Week 36 or EOT2	FAS	
2.3.4.3	Summary of Proportion of Participants Who Achieved UAS7 = 0 at Week 12 and Maintained Their Response at Every Visit Through to Week 36 or EOT2	FAS	

Table No.	Title	Population	Standard
2.3.13.1	Summary of Proportion of Participants Requiring Treatment of Chronic Spontaneous Urticaria With Corticosteroids From Baseline Up to Week 36	FAS	
2.3.13.2	Summary of Proportion of Participants Requiring Rescue Treatment of Chronic Spontaneous Urticaria With Additional Second-Generation H1 Antihistamines From Baseline Up to Week 36	FAS	
2.3.13.3	Summary of Time to First Use of Rescue Medication From Baseline Up to Week 36	FAS	
2.3.13.4	Summary of Proportion of Participants Using Rescue Medication During the Post-Treatment Follow-Up Period (EOT2 to EOS)	Post-Treatment-Evaluable	
2.3.13.5	Summary of Time to Use of Rescue Medication During the Post-Treatment Follow-Up Period (EOT2 to EOS)	Post-Treatment-Evaluable	
Safety			
3.1.1.x	Summary of Exposure During the PC Period	Safety/EXT-Evaluable	X
3.1.1.3	Summary of Exposure for Participants Who Received Only Povorcitinib Throughout Study Participation (Overall Period)	Safety	X
3.1.2.x	Summary of Study Drug Compliance During the PC Period	Safety/EXT-Evaluable	X
3.2.1.x	Overall Summary of Treatment-Emergent Adverse Events During the PC Period	Safety/EXT-Evaluable	X
3.2.1.3	Overall Summary of Treatment-Emergent Adverse Events for Participants Who Received Only Povorcitinib During Study Participation	Safety	X
3.2.2.x	Summary of Treatment-Emergent Adverse Events by MedDRA System Organ Class and Preferred Term During the PC Period	Safety/EXT-Evaluable	X
3.2.2.3	Summary of Treatment-Emergent Adverse Events by MedDRA System Organ Class and Preferred Term for Participants Who Received Only Povorcitinib During Study Participation	Safety	X
3.2.3.x	Summary of Treatment-Emergent Adverse Events by MedDRA Preferred Term in Decreasing Order of Frequency During the PC Period	Safety/EXT-Evaluable	X

Table No.	Title	Population	Standard
3.2.3.3	Summary of Treatment-Emergent Adverse Events by MedDRA Preferred Term in Decreasing Order of Frequency for Participants Who Received Only Povorcitinib During Study Participation	Safety	X
3.2.4.x	Summary of Treatment-Emergent Adverse Events by MedDRA System Organ Class, Preferred Term, and Maximum Severity During the PC Period	Safety/EXT-Evaluable	X
3.2.4.3	Summary of Treatment-Emergent Adverse Events by MedDRA System Organ Class, Preferred Term, and Maximum Severity for Participants Who Received Only Povorcitinib During Study Participation	Safety	X
3.2.5.x	Summary of Treatment-Emergent Adverse Events by MedDRA System Organ Class, Preferred Term, and CTCAE Grade Category During the PC Period	Safety/EXT-Evaluable	X
3.2.5.3	Summary of Treatment-Emergent Adverse Events by MedDRA System Organ Class, Preferred Term, and CTCAE Grade Category for Participants Who Received Only Povorcitinib During Study Participation	Safety	X
3.2.6.x	Summary of Grade 3 or Higher Treatment-Emergent Adverse Events by MedDRA System Organ Class and Preferred Term During the PC Period	Safety/EXT-Evaluable	X
3.2.6.3	Summary of Grade 3 or Higher Treatment-Emergent Adverse Events by MedDRA System Organ Class and Preferred Term for Participants Who Received Only Povorcitinib During Study Participation	Safety	X
3.2.7.x	Summary of Grade 3 or Higher Treatment-Emergent Adverse Events by MedDRA Preferred Term in Decreasing Order of Frequency During the PC Period	Safety/EXT-Evaluable	X
3.2.7.3	Summary of Grade 3 or Higher Treatment-Emergent Adverse Events by MedDRA Preferred Term in Decreasing Order of Frequency for Participants Who Received Only Povorcitinib During Study Participation	Safety	X
3.2.8.x	Summary of Serious Treatment-Emergent Adverse Events by MedDRA System Organ Class and Preferred Term During the PC Period	Safety/EXT-Evaluable	X
3.2.8.3	Summary of Serious Treatment-Emergent Adverse Events by MedDRA System Organ Class and Preferred Term for Participants Who Received Only Povorcitinib During Study Participation	Safety	X
3.2.9.x	Summary of Serious Treatment-Emergent Adverse Events by MedDRA Preferred Term in Decreasing Order of Frequency During the PC Period	Safety/EXT-Evaluable	X
3.2.9.3	Summary of Serious Treatment-Emergent Adverse Events by MedDRA Preferred Term in Decreasing Order of Frequency for Participants Who Received Only Povorcitinib During Study Participation	Safety	X
3.2.10.x	Summary of Treatment-Related Treatment-Emergent Adverse Events by MedDRA System Organ Class and Preferred Term During the PC Period	Safety/EXT-Evaluable	X

Table No.	Title	Population	Standard
3.2.10.3	Summary of Treatment-Related Treatment-Emergent Adverse Events by MedDRA System Organ Class and Preferred Term for Participants Who Received Only Povorcitinib During Study Participation	Safety	X
3.2.11.x	Summary of Treatment-Related Treatment-Emergent Adverse Events by MedDRA Preferred Term in Decreasing Order of Frequency During the PC Period	Safety/EXT-Evaluable	X
3.2.11.3	Summary of Treatment-Related Treatment-Emergent Adverse Events by MedDRA Preferred Term in Decreasing Order of Frequency for Participants Who Received Only Povorcitinib During Study Participation	Safety	X
3.2.12.x	Summary of Grade 3 or Higher Treatment-Related Treatment-Emergent Adverse Events by MedDRA System Organ Class and Preferred Term During the PC Period	Safety/EXT-Evaluable	X
3.2.12.3	Summary of Grade 3 or Higher Treatment-Related Treatment-Emergent Adverse Events by MedDRA System Organ Class and Preferred Term for Participants Who Received Only Povorcitinib During Study Participation	Safety	X
3.2.13.x	Summary of Treatment-Related Serious Treatment-Emergent Adverse Events by MedDRA System Organ Class and Preferred Term During the PC Period	Safety/EXT-Evaluable	X
3.2.13.3	Summary of Treatment-Related Serious Treatment-Emergent Adverse Events by MedDRA System Organ Class and Preferred Term for Participants Who Received Only Povorcitinib During Study Participation	Safety	X
3.2.14.x	Summary of Treatment-Emergent Adverse Events with a Fatal Outcome by MedDRA System Organ Class and Preferred Term During the PC Period	Safety/EXT-Evaluable	X
3.2.14.3	Summary of Treatment-Emergent Adverse Events with a Fatal Outcome by MedDRA System Organ Class and Preferred Term for Participants Who Received Only Povorcitinib During Study Participation	Safety	X
3.2.15.x	Summary of Treatment-Emergent Adverse Events Leading to Dose Interruption by MedDRA System Organ Class and Preferred Term During the PC Period	Safety/EXT-Evaluable	X
3.2.15.3	Summary of Treatment-Emergent Adverse Events Leading to Dose Interruption by MedDRA System Organ Class and Preferred Term for Participants Who Received Only Povorcitinib During Study Participation	Safety	X
3.2.16.x	Summary of Treatment-Emergent Adverse Events Leading to Discontinuation of Study Drug by MedDRA System Organ Class and Preferred Term During the PC Period	Safety/EXT-Evaluable	X
3.2.16.3	Summary of Treatment-Emergent Adverse Events Leading to Discontinuation of Study Drug by MedDRA System Organ Class and Preferred Term for Participants Who Received Only Povorcitinib 15,45, or 75 mg During Study Participation	Safety	X
3.2.17.x	Summary of Treatment-Emergent Adverse Events of Special Interest by Category and MedDRA Preferred Term During the PC Period	Safety/EXT-Evaluable	

Table No.	Title	Population	Standard
3.2.17.3	Summary of Treatment-Emergent Adverse Events of Special Interest by Category and MedDRA Preferred Term for Participants Who Received Only Povorcitinib During Study Participation	Safety	
3.2.18.x	Summary of Treatment-Emergent Adverse Events of Special Interest Leading to Dose Interruption by Category and MedDRA Preferred Term During the PC Period	Safety/EXT-Evaluable	
3.2.18.3	Summary of Treatment-Emergent Adverse Events of Special Interest Leading to Dose Interruption by Category and MedDRA Preferred Term During the Overall Study Period for Participants Who Received Only Povorcitinib During Study Participation	Safety	
3.2.19.x	Summary of Treatment-Emergent Adverse Events of Special Interest Leading to Discontinuation of Study Drug by Category and MedDRA Preferred Term During the PC Period	Safety/EXT-Evaluable	
3.2.19.3	Summary of Treatment-Emergent Adverse Events of Special Interest Leading to Discontinuation of Study Drug by Category and MedDRA Preferred Term During the Overall Study Period for Participants Who Received Only Povorcitinib During Study Participation	Safety	
3.2.20.x	Summary of Treatment-Emergent Events of Clinical Interest (PT Component) by Category and MedDRA Preferred Term During the PC Period	Safety/EXT-Evaluable	
3.2.20.3	Summary of Treatment-Emergent Events of Clinical Interest (PT Component) by Category and MedDRA Preferred Term for Participants Who Received Only Povorcitinib During Study Participation	Safety	
3.3.1.1.x	Summary of Laboratory Values - Hematology	Safety/EXT-Evaluable	X
3.3.1.2.x	Summary of Laboratory Values - Chemistry	Safety/EXT-Evaluable	X
3.3.1.3.x	Summary of Laboratory Values - Lipid Panel	Safety/EXT-Evaluable	X
3.3.1.4	Summary of Laboratory Values - Coagulation	Safety/EXT-Evaluable	X
3.3.1.5	Summary of Laboratory Values - Other	Safety/EXT-Evaluable	X
3.3.2.1.x	Shift Summary of Hematology Laboratory Values - to the Worst Abnormal Value	Safety/EXT-Evaluable	X
3.3.2.2.x	Shift Summary of Chemistry Laboratory Values - to the Worst Abnormal Value	Safety/EXT-Evaluable	X
3.3.2.3.1	Shift Summary of Lipid Panel Laboratory Values - to the Worst Abnormal Value	Safety	X
3.3.3.1.x	Shift Summary of Hematology Laboratory Values in CTCAE Grade - to the Worst Grade Abnormal Value	Safety/EXT-Evaluable	X
3.3.3.2.x	Shift Summary of Chemistry Laboratory Values in CTCAE Grade - to the Worst Grade Abnormal Value	Safety/EXT-Evaluable	X
3.3.3.3.1	Shift Summary of Lipid Panel Laboratory Values in CTCAE Grade - to the Worst Grade Abnormal Value	Safety	X

Table No.	Title	Population	Standard
3.3.4.x	Summary of Potentially Clinically Important Laboratory Values by Visit	Safety/EXT-Evaluable	X
3.3.5.x	Summary of Potential Drug-Induced Liver Injury Events by Visit	Safety/EXT-Evaluable,	
3.4.1.x	Summary of Systolic Blood Pressure During the PC Period	Safety/EXT-Evaluable	X
3.4.2.x	Summary of Diastolic Blood Pressure During the PC Period	Safety/EXT-Evaluable	X
3.4.3.x	Summary of Pulse During the PC Period	Safety/EXT-Evaluable	X
3.4.4.x	Summary of Respiratory Rate During the PC Period	Safety/EXT-Evaluable	X
3.4.5.x	Summary of Body Temperature During the PC Period	Safety/EXT-Evaluable	X
3.5.1.1.x	Summary of PR Interval (ms) From 12-Lead ECG by Visit During the PC Period	Safety/EXT-Evaluable	X
3.5.1.2.x	Summary of QRS Interval (ms) From 12-Lead ECG by Visit During the PC Period	Safety/EXT-Evaluable	X
3.5.1.3.x	Summary of QT Interval (ms) From 12-Lead ECG by Visit During the PC Period	Safety/EXT-Evaluable	X
3.5.1.4.x	Summary of QTcF Interval (ms) From 12-Lead ECG by Visit During the PC Period	Safety/EXT-Evaluable	X
3.5.1.5.x	Summary of Heart Rate (bpm) From 12-Lead ECG by Visit During the PC Period	Safety/EXT-Evaluable	X
3.5.1.6.x	Summary of Clinically Significant ECG Abnormality by Visit During the PC Period	Safety/EXT-Evaluable	X

